**Table 7: Descriptive statistics for outcome variables**

Outcome Variables	Group		P-value	Effect size
	Paxlovid	Control		
Hospitalizations, % (n)				
Number of hospitalizations per patient, mean (SD)				
Number of hospitalizations per patient among patients with readmissions, % (n)				
Time to first outpatient encounter, mean (SD)				
ICU Admission, % (n)				
Hospital Length of Stay, mean (SD)				
ICU/Non-ICU LOS, mean (SD)				
IMV/No IMV LOS, mean (SD)				
Treatment				
IMV Usage, % (n)				
Supplemental Oxygen Usage, % (n)				
Non-invasive Ventilation Usage, % (n)				
High-flow Nasal Cannula Usage, % (n)				
Hospital Discharge Status				
Went home, % (n)				
Transfer to skilled nursing facility, % (n)				

PFIZER CONFIDENTIAL

CT24-WI-GL03-RF03 2.0 *Non-Interventional Statistical Analysis Plan For Secondary Data Collection Study* 01-Jun-2020

Page 20 of 22

Transfer to other healthcare facility, % (n)				
Transfer to other long-term care facility, % (n)				
Transfer to hospice, % (n)				
Death, % (n)				
Medication Usage, % (n)				
Antibiotic, % (n)				
Antiviral (incl. Paxlovid, COVID-19 monoclonal antibodies), % (n)				
Antithrombotic, % (n)				
Anti-inflammatory (incl. steroids), % (n)				

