**Table 4. HRU Data**

Variable	Operational definition
Hospital Length of Stay	The total length of stay (LOS) recorded for all hospitalizations during the baseline period and follow-up period in days (excluding within 24 hours of Paxlovid™ initiation).
ICU/Non-ICU LOS	The total number of days in the intensive care unit (ICU) and the number of days that were not spent in the ICU (non-ICU) recorded for all hospitalizations during the baseline period and follow-up period in days (excluding within 24 hours of Paxlovid™ initiation).
IMV/No IMV LOS	The total number of days with and without invasive mechanical ventilation (IMV) recorded for all hospitalizations during the baseline period and follow-up period in days (excluding within 24 hours of Paxlovid™ initiation).
Hospitalizations (Count and Percentage)	The count and percentage of patients with all-cause and COVID-related hospitalizations (excluding within 24 hours of Paxlovid™ initiation) during the baseline and follow-up period.
Number of Hospitalizations per Patient	The number of hospitalizations per patient in the baseline and follow-up periods for all-cause and COVID-related hospitalizations (excluding within 24 hours of Paxlovid™ initiation) will be described.
Number of Hospitalizations per Patient among Patients with Readmissions	The number of all-cause and COVID-related hospitalizations (excluding within 24 hours of Paxlovid™ initiation) per patient in the baseline and follow-up periods will be described among patients with readmissions during the same period. The cause for readmission will be reported when available.
Time to First Outpatient Encounter	Time from COVID-19 diagnosis to the earliest outpatient encounter to occur after diagnosis during the baseline period.

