## 1.2 STUDY OBJECTIVES

The overall aim of this study is to examine the baseline demographic, clinical, and outcome characteristics of COVID-19 patients who received Paxlovid.

PFIZER CONFIDENTIAL

CT24-WI-GL03-RF03 2.0 *Non-Interventional Statistical Analysis Plan For Secondary Data Collection*  
*Study 01-Jun-2020*  
Page 6 of 22

The objectives are

- (i) to describe the demographic, clinical, and outcome characteristics of COVID-19 patients who received Paxlovid and COVID-19 patients who were offered, but refused Paxlovid
- (ii) to examine differences in the demographic characteristics (e.g., age, sex, nationality, type of outpatient encounter, vaccination status) between COVID-19 patients who received Paxlovid and COVID-19 patients who refused Paxlovid,
- (iii) to examine differences in the clinical characteristics (e.g., comorbidities, symptoms, duration of symptoms) between COVID-19 patients who received Paxlovid and COVID-19 patients who refused Paxlovid over a five-day follow-up,
- (iv) to examine differences in outcomes (e.g., hospitalisations, time spent in an intensive care unit, time spent with invasive mechanical ventilation, supplemental oxygen usage, re-admission to hospital, deaths) between COVID-19 patients who received Paxlovid and COVID-19 patients who refused Paxlovid over a five-day follow-up.
- (v) To examine differences in the proportion of COVID-19 patients who meet the most up-to-date WHO recommendations for the use of therapeutics in the treatment of COVID-19 (ie, version 14, published 10Nov2023) in comparison to Kingdom of Bahrain national recommendations.

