**Table 4: COVID-19 disease outcome variables**

Variable	Operational definition
Hospitalizations	Number of all-cause and COVID-related hospitalizations (excluding within 24 hours of Paxlovid initiation) during the baseline and follow-up period per patient
Number of Hospitalizations per Patient	The number of hospitalizations per patient in the baseline and follow-up periods for all-cause and COVID-related hospitalizations (excluding within 24 hours of Paxlovid initiation)
Number of Hospitalizations per Patient among Patients with Readmissions	The number of all-cause and COVID-related hospitalizations (excluding within 24 hours of Paxlovid initiation) per patient in the baseline and follow-up periods will be described among patients with readmissions during the same period. The cause for readmission will be reported when available.
Time to First Outpatient Encounter	Time from COVID-19 diagnosis to the earliest outpatient encounter to occur after diagnosis during the baseline period.

PFIZER CONFIDENTIAL

Hospital Length of Stay	The total length of stay (LOS) recorded for all hospitalizations during the baseline period and follow-up period in days (excluding within 24 hours of Paxlovid initiation)
ICU/Non-ICU LOS	The total number of days in the intensive care unit (ICU) and the number of days that were not spent in the ICU (non-ICU) recorded for all hospitalizations during the baseline period and follow-up period in days (excluding within 24 hours of Paxlovid initiation)
IMV/No IMV LOS	The total number of days with and without invasive mechanical ventilation (IMV) recorded for all hospitalizations during the baseline period and follow-up period in days (excluding within 24 hours of Paxlovid initiation)
ICU Admission	ICU admission during COVID-related hospitalizations in the baseline and follow-up periods (excluding within 24 hours of Paxlovid initiation)
IMV Usage	IMV (i.e., intubation and mechanical ventilation) usage, including extracorporeal membrane oxygenation (ECMO), during COVID-related hospitalizations in the baseline and follow-up periods (excluding within 24 hours of Paxlovid initiation)
Supplemental Oxygen Usage	supplemental oxygen usage during COVID-related hospitalizations in the baseline and follow-up periods (excluding within 24 hours of Paxlovid initiation)

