## 1.13 STATISTICAL ANALYSES

### Descriptive statistics

Categorical variables will be presented in terms of raw numbers (n) and percentages (%). Continuous variables will be presented as means and standard deviations or as medians and interquartile ranges, depending on the level of skewness and kurtosis of the data.

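### SAP objective (iv) asks for a comparison of readmission, but the only readmission variable counts admissions among patients already readmitted, and its table row has a format that does not fit a count

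*SAP*

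**What the plan says.** SAP section 1.2, objective (iv), is to examine group differences in outcomes over a five-day follow-up. Its list of examples includes "re-admission to hospital, deaths) between COVID-19 patients who received Paxlovid" and those who refused it.

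SAP Table 4 has one variable on readmission. It is the number of all-cause and COVID-related hospitalizations "per patient in the baseline and follow-up periods will be described among patients with readmissions during the same period". Protocol Table 4 has the same variable under the name "Number of Hospitalizations per Patient among Patients with Readmissions".

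The shell for SAP Table 7 has three rows that bear on this:

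- "Hospitalizations, % (n" and its closing bracket, for any hospitalization
- "Number of hospitalizations per patient, mean (SD" and its closing bracket, for the count per patient
- "Number of hospitalizations per patient among patients with readmissions, % (n" and its closing bracket, for the count restricted to readmitted patients

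Table 7 has P-value and effect-size columns. On format, SAP section 1.13 says "Categorical variables will be presented in terms of raw numbers (n) and percentages"; means with SDs, or medians with IQRs, are for continuous variables. The same section promises differences in proportions or means with 95% confidence intervals.

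**The concern.** To compare readmission between groups, the table needs the number of patients readmitted in each group over a stated denominator. No SAP variable or table row is defined that way. The readmission variable starts from patients who have already been readmitted and asks how many admissions they had. That is a different question, and its answer need not move when the readmission risk moves.

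In the follow-up period the restriction selects patients on something that happened after the index date. The two subsets compared are therefore no longer the treated and control groups.

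The shell then asks for % (n) where the definition gives a count. A programmer must choose between following the definition and following the format. Depending on that choice, an outcome named in the objective is either not reported or is reported under a label that does not describe it.

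**Working it through.** The plan states no readmission rate, power or expected count, so there is no figure to reproduce. The check sets the texts side by side and then illustrates the consequence.

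**1. Objective, definition and shell**

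| Place | What it calls for |
|---|---|
| SAP 1.2, objective (iv) | Difference between groups in readmission |
| SAP Table 4 (and protocol Table 4) | Hospitalizations per patient, among readmitted patients only, baseline and follow-up |
| SAP Table 7, readmission row | The same count, formatted % (n), with P-value and effect size |
| SAP Table 7, row above | Count per patient, formatted mean (SD) |
| SAP 1.13 | n and % for categorical variables |

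The definition does not deliver what the objective asks, and the format does not fit the definition. No denominator is given for the percentage.

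**2. Illustration of the defined count in follow-up**

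Inputs: about 3000 treated and 1000 control patients (SAP, Study population). Assumptions: the readmission counts below, and exactly two admissions for each readmitted patient.

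- Defined count = admissions among readmitted patients / number readmitted.
- Patient-level risk = number readmitted / patients in the group.
- Difference = treated minus control, with a Newcombe 95% CI and a two-sided Fisher p.

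| Readmitted, treated and control | Defined count | Risk, treated and control | Difference in points (95% CI) | Fisher p |
|---|---|---|---|---|
| 9/3000 and 9/1000 | 18/9 = 2.0 and 18/9 = 2.0 | 0.3% and 0.9% | −0.6 (−1.4 to −0.1) | 0.025 |
| 9/3000 and 6/1000 | 18/9 = 2.0 and 12/6 = 2.0 | 0.3% and 0.6% | −0.3 (−1.0 to 0.1) | 0.23 |
| 9/3000 and 3/1000 | 18/9 = 2.0 and 6/3 = 2.0 | 0.3% and 0.3% | 0.0 (−0.6 to 0.3) | 1.00 |

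The defined count is the same in all three rows, while the risk ratio runs from 0.33 to 1. With every value equal to 2 the pooled SD is 0, so Cohen's d and the t statistic cannot be calculated.

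The interval method matters with so few events. A Wald interval for the first row is −1.2 to 0.02 points, which includes zero although the Newcombe interval does not.

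**3. How many patients the row might rest on**

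Expected number readmitted = group size × hospitalization rate × readmission share. The rates of 0.5%, 3% and 6% are the WHO risk-group estimates quoted in the SAP, which gives no time window for them. The 5% to 20% readmission share is an assumption.

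| Hospitalization rate | Treated (3000) | Control (1000) |
|---|---|---|
| 0.5% | 0.75 to 3 | 0.25 to 1 |
| 3% | 4.5 to 18 | 1.5 to 6 |
| 6% | 9 to 36 | 3 to 12 |

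For example, 3000 × 0.03 × 0.05 = 4.5 and 3000 × 0.03 × 0.20 = 18. Admission, discharge and readmission all within five days would probably be rarer still.

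**The case against.** The strongest reply is that % (n) was meant as the number and share of patients readmitted. The row would then answer the objective and only its wording would be at fault. A reader might otherwise infer that the row cannot show any difference in readmission. The documents do not support that: it holds when the definition is followed and a count is printed, but the format permits the other reading. What stands is that neither the row label nor the SAP Table 4 definition states that reading, and no denominator is given. The row needs correcting on either reading.

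A reader might also infer that the count is almost always 2. That is plausible for a short follow-up, but the definition also covers baseline, which protocol section 9.3 sets at one year before index. Patients with comorbidities may have three or more admissions in a year. The criticism about conditioning on a post-index event likewise applies only to follow-up.

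The neighbouring rows help in part. In follow-up, total admissions minus patients hospitalized gives the number of repeat admissions. That is not the number of patients readmitted, and it comes without a comparison or an interval.

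Finally, readmission is one example in a list, it is not named in the protocol objectives, and the SAP calls the work exploratory. This limits the weight of the point. It does not remove it, because the SAP names readmission for comparison and sets alpha at 0.05 for all tests.

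**Conclusion.** The point holds as a mismatch between objective, definition and table shell. Followed as written, the definition yields a count among readmitted patients, not the readmission risk by group, and the % (n) label contradicts that definition.

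The size of the effect on results cannot be taken from the documents, which give no readmission rate. Under the assumed counts, the defined quantity is 2.0 against 2.0 whether the risk is 0.3% against 0.9% or 0.3% against 0.3%.

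A reader might infer that the present row hides a significant difference. The documents do not support this. With 9/3000 against 6/1000 the correct row gives p = 0.23 and an interval that includes zero. The defect is the wrong estimand, not lost power. It should be corrected, but it concerns one outcome in an exploratory analysis.

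**What to change.** 1. Add to SAP Table 7 the row *Patients with at least one readmission in the follow-up period, % (n)*, with all patients in the group as denominator. The same figure among hospitalized patients can be added. Report the difference in proportions with the 95% CI that section 1.13 already promises, and name an interval method suited to few events.
2. Add the matching definition to SAP Table 4. State what counts as a readmission, and report all-cause and COVID-related readmissions.
3. Tie the row to the follow-up window once the five days in SAP objectives (iii) and (iv) and the 28 days in protocol section 8 and protocol Table 1 are reconciled. Report any baseline readmissions separately.
4. Relabel the existing row as mean (SD) or median (IQR), descriptive among readmitted patients, without a p-value or effect size.

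The cost is one extra table row and one definition. Hospitalizations are already to be extracted, so no new data source is needed.

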**Table 8: Comparison of WHO and Bahrain national recommendation for Paxlovid Treatment in COVID-19 patients**

Outcome Variables	WHO recommendation for Paxlovid treatment		Bahrain national recommendation for Paxlovid treatment
	Strongly recommended	Conditionally recommended	Strongly recommended
All COVID patients			
Paxlovid group			
Control group			

